### 3.1.3 Part 2 / Confirmatory Efficacy/Safety Evaluation

Part 2 of the trial will consist of a screening period of up to a maximum of 5 weeks, a 12 week, parallel group, placebo-controlled, double-blind intravenous induction therapy period, and a 12 week safety follow-up period for patients not rolling-over into subsequent maintenance study 1368-0020.

Approximately 390 eligible patients with moderate to severe UC who have failed previous biologic treatments in the past will be randomised in a 1:1:1 ratio to one of the 3 following treatment groups:

Group 1: Placebo i.v. q4w	(n= 130)
Group 2: BI655130 (SPESOLIMAB) selected low dose i.v. q4w	(n= 130)
Group 3: BI655130 (SPESOLIMAB) selected high dose i.v. q4w	(n= 130)

For the dose selection process for part 2 cf. [Section 3.1.2](#).

Randomization will be stratified by previous BIO treatment failure and concomitant corticosteroid therapy at visit 2/randomization. In addition, a stratification for Japan versus non-Japan will be done in order to assure that sufficient patients per treatment group are recruited specifically to support individual country submission in Japan; this strata will be treated as an operational strata and will not be included into the analyses of the primary endpoint. Screening of patients who have failed TNF $\alpha$  antagonists-AND-Vedolizumab will be closed once 117 patients have been randomized into this stratum (cf. [Section 4.1.3](#)).

Part 2 will be one of two independent trials to confirm the efficacy and safety of induction treatment with BI655130 (SPESOLIMAB) in a randomized, double-blind, placebo controlled design. This part is assumed to have an identical population to that of Part 1 and will initiate, once review of the completed Part 1 data has been performed and

decision on part 2 doses has been taken. This scenario is fully dependent upon the pre-defined decision criteria for Part 1 having been successfully met (see [Section 3.1.2](#)).

Patients who discontinue study drug early will be followed up in this study until 16 weeks after last study drug administration, while patients who complete the 12-week primary endpoint assessment in part 2 of this study will enter the pivotal maintenance trial 1368-0020, which offers a randomized maintenance treatment guided by the outcome of Part 2 of the induction trial:

- patients on BI655130 (SPESOLIMAB) treatment who meet the clinical response endpoint (cf. [Section 5.1](#)) at week 12 will be entered into the double-blind, placebo controlled randomised withdrawal study (1368-0020) and randomized to receive subcutaneous treatment with BI655130 (SPESOLIMAB) or placebo until week 52.
- patients on placebo treatment who meet the clinical response endpoint (cf. [Section 5.1](#)) at week 12 will be entered into the double-blind, placebo controlled randomised withdrawal study (1368-0020) and mock-randomized to receive subcutaneous treatment with placebo until week 52.
- patients not achieving a clinical response (whether on active drug or placebo) will undergo a further 12 weeks open label i.v. re-induction with BI655130 (SPESOLIMAB) in study 1368-0020, after which eligibility will be re-assessed. Patients who subsequently meet the clinical response definition, will be randomized into the randomized withdrawal part of study 1368-0020, while non-responders will be discontinued from the trial 1368-0020.

#### 3.1.4 Follow-up period:

After completion of treatment period, those patients not rolling over into one of the maintenance trials (1368-0017 or 1368-0020) will continue safety follow-up for an additional 12 weeks after the Visit 6. This observation period covers 16 weeks after the last dose of BI655130 (SPESOLIMAB) which represents around 4-5 half lives of BI655130 (SPESOLIMAB).

### 3.2 DISCUSSION OF TRIAL DESIGN, INCLUDING THE CHOICE OF CONTROL GROUP(S)

This operationally seamless trial design, with separate proof-of-concept (Part 1, phase II) and confirmation of efficacy and safety parts (Part 2, phase III), will include pre-defined decision criteria for continuing BI655130 (SPESOLIMAB) doses from Part 1 into Part 2 (see [Section 3.1.2](#)), with the intent of ensuring that a positive proof-of-concept will quickly be followed by the confirmation of efficacy and safety of this new compound with its unique dual mode-of-action in patients with ulcerative colitis. Should Part 1 results, however, indicate the need for design modifications in Part 2 beyond those pre-specified in the protocol (i.e. pre-specified dose selection), then initiation of Part 2 may be postponed until the required modifications have been implemented via a global CTP amendment (e.g. other dose regimens or endpoints).

A parallel group, randomized, double-blind and placebo controlled trial was considered most appropriate to demonstrate PoC, while a PK/PD modelling approach will be employed to select two doses for subsequent confirmation of the efficacy and safety of BI655130 (SPESOLIMAB). The placebo control group in Parts 1 and 2 is thus required to compare both efficacy and safety of BI655130 (SPESOLIMAB) in patients with moderate-to-severely active ulcerative colitis who failed previous biologic treatments. However, all placebo patients failing induction treatment will be offered open label active re-induction treatment as part of the subsequent maintenance trials.

The selection of target patients with moderate-to-severely active ulcerative colitis who failed at least one previous biologic treatment (defined as an inadequate response or loss of response to TNF antagonists and/or vedolizumab) is based on the high unmet medical need in such patients, where persistent mucosal inflammation is associated with an increased risk of disease progression, colon cancer and other complications.

The treatment duration of 12 weeks with BI655130 (SPESOLIMAB) was selected for both parts to exceed the 4-8 weeks duration of induction treatment reflected in the labels of biologics currently approved for IBD [[R15-4915](#), [R17-1974](#)]. This duration has been extended with the aim to maximize treatment efficacy and inform on the optimal induction duration with this new mode of action.

The three active induction dose regimens in part 1 of 300mg i.v. SD, 450mg i.v. q4w and 1200mg i.v. q4w have been selected to represent one partially effective (300mg SD) and two effective dose schedules, based on receptor occupancy rates, ITE and PK/PD results from phase I studies (cf. [Section 4.1.2](#)). Part 1 will allow to establish proof-of-concept and dose/exposure-response relationship, and thus to select the optimal dose regimens for Part 2 of this trial. Part 2 will investigate the two most efficacious, tolerable and safe doses from the Part 1 regimens, unless an unexpected safety or efficacy finding requires dose modification beyond the pre-specified transition scenarios in [Section 3.1.2](#) per CTP amendment.

Thus, this trial design is considered adequate to achieve the objectives outlined above.

### 3.3 SELECTION OF TRIAL POPULATION

Screening of patients for this trial is competitive, i.e. screening for the trial will stop at all sites at the same time once a sufficient number of patients has been screened. Investigators will be notified about screening completion and will then not be allowed to screen additional patients for this trial.

A log of all patients enrolled into the trial (i.e. who have signed informed consent) will be maintained in the ISF at the investigational site irrespective of whether they have been treated with investigational drug or not.

### 3.3.1 Main diagnosis for trial entry

Patients with moderate-to-severely active ulcerative colitis who have failed previous biologic treatments.

Please refer to [Section 8.3.1](#) (Source Documents) for the documentation requirements pertaining to the in- and exclusion criteria.

### 3.3.2 Inclusion criteria

Each patient must meet all of the following inclusion criteria to be included into the trial:

1. 18 - 75 years, at date of signing informed consent, males or females
2. Diagnosis of ulcerative colitis  $\geq 3$  months prior to screening by clinical and endoscopic evidence corroborated by a histopathology report
3. Moderate to severe activity (total MCS 6 to 12 with a RBS  $\geq 1$  AND an SFS  $\geq 1$  AND mESS  $\geq 2$  within 7-28 days prior to first dose)
4. Endoscopic activity extending proximal to the rectum ( $\geq 15$  cm from anal verge)
5. Well-documented demonstration of inadequate response or loss of response or have had unacceptable side effects with approved doses of TNF $\alpha$  antagonists (infliximab, adalimumab, golimumab) and/or vedolizumab in the past as per definition in the CTP [Appendix 10.6](#) (screening of both TNF $\alpha$  antagonists-AND-Vedolizumab failure patients will be capped once 48 randomized patients in Part 1 and 117 randomized patients in Part 2 meet this criterion; patients who have already been screened at the time of the cap will continue to be randomized into the study)
6. May be receiving a therapeutic dose of the following:
  - Oral 5-ASA compounds, provided that dose has been stable for at least the 4 weeks immediately prior to randomisation, and/or
  - Oral corticosteroids ( $\leq 20$  mg per day of prednisone or equivalent), provided that dose has been stable for the 2 weeks immediately prior to randomisation, and/or
  - Oral budesonide ( $\leq 9$  mg per day) or beclomethasone dipropionate ( $\leq 5$  mg per day), provided that dose has been stable for the 2 weeks immediately prior to randomisation, and/or
  - Azathioprine, 6-MP or methotrexate, provided that dose has been stable for the 8 weeks immediately prior to randomisation.
  - Probiotics (e.g. *S. boulardii*) provided that dose has been stable for the 4 weeks immediately prior to randomisation.
7. Patients with extensive colitis or pancolitis of  $>10$  years duration or family history of colorectal cancer or personal history of increased colorectal cancer risk must have had a negative colorectal cancer screening within  $<1$  year prior to enrolment (otherwise to be done during screening colonoscopy).
8. Women of childbearing potential (WOCBP) must be ready to use highly effective methods of birth control per ICH M3 (R2) that result in a low failure rate of less than 1% per year when used consistently and correctly. A list of contraception methods

meeting these criteria is provided in [Section 4.2.2.2](#) Restrictions regarding women of childbearing potential *Note: A woman is considered of childbearing potential (WOCBP), i.e. fertile, following menarche and until becoming postmenopausal unless permanently sterile. Permanent sterilisation methods include hysterectomy, bilateral salpingectomy and bilateral oophorectomy. Tuba ligation is NOT a method of permanent sterilisation. A postmenopausal state is defined as no menses for 12 months without an alternative medical cause.*

9. Signed and dated written informed consent for 1368.5, in accordance with GCP and local legislation prior to admission into the trial

### 3.3.3 Exclusion criteria

#### 3.3.3.1 Gastrointestinal Exclusion Criteria

Patients meeting any of these exclusion criteria must not be enrolled into the trial:

1. Evidence of abdominal abscess at screening
2. Evidence of fulminant colitis or toxic megacolon at screening
3. Ileostomy, colostomy, or known fixed symptomatic stenosis of the intestine
4. Treatment with:
  - any non-biologic medication (e.g. cyclosporine, tacrolimus or mycophenolate mofetil, intravenous corticosteroids, tofacitinib), other than those allowed per inclusion criteria, which is listed in [Section 4.2.2](#) within 30 days prior to randomisation
  - any biologic treatment with a TNF $\alpha$  antagonist (adalimumab, infliximab, golimumab, certolizumab) or vedolizumab within 8 weeks prior to randomisation. (If drug level testing for previously used biologic treatment confirms no detectable drug level before randomization, patient can be enrolled despite not having completed 8 weeks from last treatment.)
  - any previous treatment with an approved dose of ustekinumab where locally approved and available.
  - rectal 5-ASA, parenteral or rectal corticosteroids (incl. budesonide) within 2 weeks prior to screening
  - any *investigational* non-biologic drug for UC (including but not limited to JAK inhibitors, S1P modulators) within 30 days prior to randomisation
  - any *investigational* biologic for UC (including IL-12 and IL-23 inhibitors; etrolizumab) within 8 weeks. (If drug level testing for previously used biologic treatment confirms no detectable drug level before randomization, patient can be enrolled despite not having completed 8 weeks from last treatment.)
  - any prior exposure to BI655130 (SPESOLIMAB), natalizumab or rituximab
5. Positive stool examinations for *C. difficile* (toxin A/B – test positive) or other intestinal pathogens < 30 days prior to screening
6. Have had previous surgery or are anticipated to require surgical intervention for UC

7. Evidence of colonic moderate/severe mucosal dysplasia or colonic adenomas, unless properly removed
8. Primary sclerosing cholangitis
9. Faecal transplant  $\leq$  30 days prior to randomisation

### 3.3.3.2 Infectious Disease Exclusion Criteria

10. Increased risk of infectious complications (e.g. recent pyogenic infection, any congenital or acquired immunodeficiency (e.g. HIV), past organ or stem cell transplantation)
11. Live or attenuated vaccination within 6 weeks prior to screening
12. Active or latent TB: Patients with a positive TB test during screening are excluded, unless:
  - Patient had previous diagnosis of active or latent TB and has completed appropriate treatment per local practice/guidelines within the last 3 years and at least 6 months before first administration of trial medication under this protocol (patients may be re-screened once to meet this criterion)
  - A positive QuantiFERON TB (Patients with suspected false positive or indeterminate QuantiFERON TB result may be re-tested once)
  - If Quantiferon not available or providing indeterminate results after repeat testing, tuberculin skin test should be performed: A tuberculin skin test positive reaction  $\geq$ 10mm ( $\geq$ 5mm if receiving  $\geq$ 15mg/d prednisone or its equivalent)
13. Relevant chronic or acute infections including active tuberculosis, human immunodeficiency virus (HIV) infection or viral hepatitis. A patient can be re-screened if the patient was treated and is cured from the acute infection.

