	After administration of any biologic agent or protein, there is a possibility of occurrence of adverse immune reactions which can be local (e.g. redness, pruritus, and or swelling at the injection site) or systemic (e.g. anaphylactic reactions).	Patients with a history of allergy/hypersensitivity to the systemically administered trial medication agent or its excipients are excluded from the trial.  In case of systemic hypersensitivity reactions including anaphylactic reaction emerging during or after administration of trial medication, the investigator should consider in accordance with severity of the reaction and local standard of care to interrupt and treat the condition. Systemic hypersensitivity reaction is defined as AESI. It is subject to close monitoring and investigators are requested assess these conditions using the criteria discussed in the statement paper from Sampson HA[ R11-4890 ].
Infections	Inhibition of the immune response with an immune-modulating biologic may increase the risk of infections.  A recent characterization of individuals with homozygous IL36R KO	Screening procedures for infections are established for this trial. Patients with any relevant chronic or acute infections including human immunodeficiency virus (HIV), viral hepatitis or tuberculosis are excluded from the trial. Treatment of infections should be initiated promptly

	
mutations revealed that normal immune function was broadly preserved suggesting that IL36 signaling pathway inhibition does not compromise host defences [R11-4890].
	
according to standards of care. Severe infections and opportunistic infections are considered AESI for this trial. These conditions and serious infections are subject to close monitoring.

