### 5.2.3 Safety laboratory parameters

Safety laboratory parameters to be assessed are listed in [Table 5.2.3:1](#). For the sampling time points please see the flowchart.

All analyses will be performed by a central laboratory, the respective reference ranges will be provided in the ISF. A local laboratory may be used for selected tests in exceptional cases. Patients should be fasting for at least 8 hours prior to the blood sample being taken (except screening visit).

Instructions regarding sample collection, sample handling/ processing and sample shipping are provided in the Laboratory Manual in the ISF.

The central laboratory will send reports to the investigator. It is the responsibility of the investigator to evaluate the laboratory reports. Clinically relevant abnormal findings as judged by the investigator will be reported as adverse events (please refer to [Section 5.2.6](#)). Laboratory results (i.e. all safety laboratory and clinical laboratory data relevant for current clinical practice) of the patients will be available in real time to the respective investigator (via laboratory reports) and to the sponsor (via the central laboratory website) and selected abnormal laboratory alerts will be flagged to the site and sent to sponsor in real time.

Clinically relevant abnormal findings will be reported as baseline conditions or AEs. A clinically relevant value may be either in- or outside the reference range. Clinically relevant abnormal laboratory test results must be confirmed using an unscheduled visit laboratory kit and should be repeated until normalization or stabilization or until an alternative explanation has been found. Abnormal laboratory values will be also graded for intensity by using RCTC Version 2.0 criteria [[R13-3515](#)].

In case the criteria for hepatic injury are fulfilled, a number of additional measures will be performed (please see [Section 5.2.6.1](#) and the DILI Checklist provided in the ISF EDC system. The amount of blood taken from the patient concerned will be increased due to this additional sampling.

Table 5.2.3: 1 Exclusionary testing

Category	Test name
Infections screening (only at screening)	Hepatitis B Surface Antigen (qualitative) Hepatitis B core Antibody HBV-DNA (quantitative, PCR)  Hepatitis C Antibodies (qualitative) HIV-1, and HIV-2 Antibody (qualitative)
TB screening	QuantiFERON®-TB 

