#### **Adverse events of special interest (AESIs)**

The term AESI relates to any specific AE that has been identified at the project level as being of particular concern for prospective safety monitoring and safety assessment within this trial, e.g. the potential for AEs based on knowledge from other compounds in the same class. AESIs need to be reported to the sponsor’s Pharmacovigilance Department within the same timeframe that applies to SAEs, please see above.

The following are considered as AESIs:

- Systemic hypersensitivity including infusion reaction and anaphylactic reaction
  - Any suspicion of severe infusion reaction and of any potential cases of anaphylaxis should be defined and assessed using the criteria discussed in the statement paper from Sampson HA ([Appendix 10.7 R11-4890](#)).
- Severe infections (according to RCTC grading in [Appendix 10.8](#))
- Opportunistic and mycobacterium tuberculosis infections
  - These include pneumocystis jirovecii, BK virus disease including PVAN, CMV, post-transplant lymphoproliferative disorder (EBV), progressive multifocal leucoencephalopathy, bartonellosis (disseminated only), blastomycosis, toxoplasmosis, coccidioidomycosis, histoplasmosis, aspergillosis (invasive only), candidiasis (invasive or pharyngeal), cryptococcosis, other invasive fungi (mucormycosis (zygomycosis, rhizopus, mucor, lichtheimia), scedosporium/pseudallescheria boydii, fusarium), legionellosis, listeria monocytogenes (invasive only), tuberculosis, nocardiosis, non-tuberculous

mycobacterium, salmonellosis (invasive only), HBV reactivation, herpes simplex (invasive only), herpes zoster, strongyloides (hyperinfection syndrome and disseminated forms only), paracoccidioides, penicillium marneffeii, sporothrix schenckii, cryptosporidium species (chronic only), microsporidiosis, leishmaniasis (visceral only), trypanosoma cruzi infection (Chagas' disease) (disseminated only), campylobacteriosis (invasive only), shigellosis (invasive only), vibriosis (invasive due to vibrio vulnificus), HCV progression [[R17-2617](#)]

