Description of change 14		Following sentence deleted: Similarly, potential drug exposure during pregnancy must be reported if a partner of a male trial participant becomes pregnant. This requires a

		written consent of the pregnant partner.
Rationale for change		No genotoxicity or demonstrated or suspected human teratogenicity/fetotoxicity of BI 655130 at subtherapeutic systemic exposure levels

## 11.2 GLOBAL AMENDMENT 2

Date of amendment		05 October 2018
EudraCT number		2017-004230-28
EU number		
BI Trial number		1368-0005
BI Investigational Product(s)		SPESOLIMAB
Title of protocol		A Phase II/III Randomized, Double-blind, Placebo-controlled, Multicenter Study to Evaluate the Safety and Efficacy of SPESOLIMAB Induction Therapy in patients with moderate-to-severely active ulcerative colitis who have failed previous biologics therapy
To be implemented only after approval of the IRB / IEC / Competent Authorities		x
To be implemented immediately in order to eliminate hazard – IRB / IEC / Competent Authority to be notified of change with request for approval		
Can be implemented without IRB / IEC / Competent Authority approval as changes involve logistical or administrative aspects only		
Section to be changed		Flow chart 1, 2
Description of change 1		Correction in calculation of trial periods
Rationale for change		Administrative
Section to be changed		Footnote #4 of Flow Chart, part 1 and part 2
Description of change 2		In addition, at Visits 2, 4 and 5 vital signs will be assessed at approximately 5 and 60 minutes after study drug administration. Changed to: In addition, at Visits 2, 4 and 5 vital signs will be assessed at approximately 5 and 60 minutes after the end of study drug administration.
Rationale for change		To clarify visit procedures
Section to be changed		Footnote #8 of Flow Chart, part 1 and part 2
Description of change 3		At study visits with study drug administration, pre-dose PK/ADA/flow cytometry ██████████ samples changed to: At study visits with study drug administration, pre-dose PK/ADA ██████████ samples
Rationale for change		Correction of statement on planned analysis
Section to be changed		Footnote #10 of Flow Chart, part 1 and part 2

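### Exclusion criterion 12 lists two definitions of a positive TB test as exceptions to the exclusion, so as written it does not exclude untreated latent TB, and SAP code ID.03 takes over the list

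*Protocol*

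**What the plan says.** Criterion 12 of Protocol 3.3.3.2 is headed as covering active or latent TB. Its stem reads "Patients with a positive TB test during screening are excluded, unless" and is followed by three bullets at the same level:

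1. Earlier active or latent TB, with adequate treatment finished within the past 3 years and at least 6 months before the first dose. One re-screening is allowed.
2. "A positive QuantiFERON TB (Patients with suspected false positive or indeterminate QuantiFERON TB result may be re-tested once".
3. "If Quantiferon not available or providing indeterminate results after repeat testing, tuberculin skin test should be performed", followed by the skin-test cut-off of 10 mm or more (5 mm or more on at least 15 mg/day of prednisone or equivalent).

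Criterion 13 separately excludes "Relevant chronic or acute infections including active tuberculosis, human immunodeficiency virus (HIV) infection or viral hepatitis".

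SAP Table 6.2: 1, code ID.03, defines the corresponding important protocol deviation. It treats test-positive patients as excluded apart from the situations that criterion 12 lists. Its column for exclusion from analysis sets reads None.

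**The concern.** Bullets 2 and 3 are not exceptions. They describe the results that should trigger the exclusion, yet they stand under the word *unless*. A site that followed the text exactly could accept a patient with a positive QuantiFERON and untreated latent TB. The deviation reviewer using ID.03 is sent to the same list and is not told which bullet is the real exception.

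What is at stake is patient safety and the classification of deviations. The benefit-risk table in Protocol 1.4 gives infection as a hypothetical risk of an immune-modulating biologic. Inclusion criterion 6 allows background corticosteroids, azathioprine, 6-MP or methotrexate. The adverse events of special interest include "Opportunistic and mycobacterium tuberculosis infections".

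**Working it through.** No arithmetic bears on the main point, so the check is a logical reading followed by a search for text elsewhere that restores the exclusion.

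**Logic of criterion 12.** Let Q be a positive QuantiFERON (bullet 2), S a skin test at or above the cut-off when QuantiFERON is unavailable or repeatedly indeterminate (bullet 3), and T previously treated TB (bullet 1). A positive test, as the criterion describes it, is Q or S.

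- As written: exclude if (Q or S) and not (T or Q or S). This can never be true.
- As evidently intended: exclude if (Q or S) and not T.

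| Patient | As written | As intended |
|---|---|---|
| Positive QuantiFERON, no earlier TB treatment | Not excluded | Excluded |
| QuantiFERON indeterminate twice, skin test at or above cut-off, no earlier TB treatment | Not excluded | Excluded |
| Positive QuantiFERON, earlier TB treated within the stated window | Not excluded | Not excluded |

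Two of the three bullets are test definitions and one is a true exception. The error reverses the outcome in the first two rows.

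**Other places that might restore the exclusion.**

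- Criterion 13 names active tuberculosis. Its list is not exhaustive, but it does not clearly reach latent TB.
- Criterion 10 (raised risk of infectious complications) and criterion 19 (a clinically significant condition or laboratory value in the investigator's opinion) could be applied. Both depend on judgement and neither mentions TB.
- Protocol 1.4 says "Patients with any relevant chronic or acute infections including human immunodeficiency virus (HIV), viral hepatitis or tuberculosis are excluded from the trial", and QuantiFERON appears under "Table 5.2.3: 1 Exclusionary testing" in Protocol 5.2.3. Both show intent, but neither is an eligibility criterion.

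No other numbered criterion explicitly excludes untreated latent TB.

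**When the wording arose.** The amendment log is used here only for dating. Global amendment 2 ("05 October 2018") changed a plain exclusion stem to the present one and placed the treated-TB bullet above the two test definitions, which stayed in the list. The log's new text shows the same three bullets, so the layout is not an artefact of reading the PDF. Global amendment 3 (09 October 2019) edited exclusion criteria 4, 5 and 14 but not 12. The interval is 365 + 4 = 369 days.

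SAP code A1.03 attaches protocol version 3.0 to the amendment-2 wording of inclusion criterion 3 and mentions patients enrolled under versions 1 and 2. By inference, patients screened under those earlier versions had the clear TB rule.

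**Number of patients.** This cannot be derived. The documents give neither a latent-TB prevalence nor a count of patients screened under version 3.0 or later.

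**The case against.** The strongest reply is that nobody would read the criterion this way. The heading names active or latent TB, and the stem of the exclusion section says that patients meeting any criterion must not be enrolled. The literal reading also defeats itself, because a positive test would excuse a positive test. The bullets themselves presuppose exclusion: re-testing a suspected false positive, re-screening to meet the criterion, and a lower skin-test cut-off on steroids make sense only if a positive result disqualifies. An investigator could also use criteria 10, 13 or 19. On the SAP side, ID.03 carries the label of active or latent TB, and SAP 6.2 already has every deviation assessed at a review meeting, which can apply the intended rule.

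Most of this stands as evidence of intent, and a site would probably act on that intent. It does not correct the operative text. Criteria 10 and 19 rest on judgement and do not name TB, and ID.03 still points to a list in which only one of three entries is an exception. Recoverable intent limits the consequence and makes the correction uncontroversial, but a safety criterion should not need the reader to repair its logic.

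**Conclusion.** The concern holds. Followed exactly, criterion 12 excludes nobody on a TB test result, no other numbered criterion clearly excludes untreated latent TB, and ID.03 inherits the defect. It should be fixed.

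The effect is confined to patient safety and deviation classification. ID.03 removes patients from 0 analysis sets, so 0 efficacy estimates change. Active TB remains excluded through criterion 13. Nothing in the documents shows that a patient with untreated latent TB was enrolled.

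The conclusion rests on reading the three bullets as one list under the stem, which is how both the current criterion and the amendment's new text present them.

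**What to change.** Reword criterion 12 so that the definitions come first and the exception stands alone, with the sponsor's medical team to confirm. For example:

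> A patient whose TB test is positive at screening is excluded. Positive means (a) a positive QuantiFERON, with one re-test allowed for a suspected false positive or an indeterminate result; or (b) where QuantiFERON cannot be done or stays indeterminate on repeat, a skin test of at least 10 mm, or at least 5 mm on 15 mg/day or more of prednisone or equivalent. The sole exception is earlier active or latent TB with adequate treatment finished in the past 3 years and at least 6 months before first dosing; one re-screening is allowed.

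This keeps the sponsor's thresholds, re-test rule and time window.

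In SAP Table 6.2: 1, have ID.03 name that single exception in place of the reference to the criterion 12 list. Check it against a listing of enrolled patients with a positive TB test before the database lock meeting. SAP Section 3 says that running Part 2 seamlessly after Part 1 is no longer viable, so these two SAP actions have the most remaining value. The protocol rewording matters for any screening still done under this protocol.

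The cost is one protocol clarification, one line in the SAP table and one listing. No extra procedures or patients are needed.
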